Consent is discussed and agreed as per the separate consent form and participant information sheet from potential participants, in-line with the inclusion and exclusion criteria. Blinding is not employed as it is impractical and would obstruct study methods. The study will take place across at least one year to include the peak periods of seasonal pathogens.

Randomisation

Participants will be enrolled and assigned a participant identification number consecutively. Once a patient has been screened and consented a study team member will log onto the password-protected electronic randomisation website (sealedenvelope.com, which uses randomised permuted blocks) to obtain a randomisation code for the patient who will then be allocated to either the intervention or control group.

For those randomised to the interventional arm:

A stool sample will be taken by a member of research staff (doctor or nurse). In the event of the patient being unable to provide a timely stool sample, a rectal swab will be obtained with appropriate chaperone as per hospital policy. The sample is placed in Carey-Blair media and analysed on the FilmArray using the Gastrointestinal Panel, as per training delivered by the apparatus manufacturer. Test results are generated in about 1 hour. In the event of a run failure, the analysis run will be repeated using the same sample; if there is insufficient sample left, further samples may be taken if the participant consents. If a rectal swab was

tested initially, a stool sample will be subsequently obtained at the earliest opportunity and then tested and the results checked to ensure concordance.

The results of the test will be documented in the patient's case notes. In the event of a pathogen being detected, a member of the clinical team responsible for the patient will be directly informed. The participant will also be informed of the result. If a positive result for a bacterial pathogen is detected the clinical team will be directed to the local and national treatment guidelines for that pathogen.

For all positive and negative results the infection and prevention control team and the site managers responsible for side room allocation will be informed in real time.

Further laboratory stool testing will be at the discretion of the responsible clinical team.

For those randomised to the control group

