These patients will be managed according to standard clinical care. Laboratory stool testing will be at the discretion of the responsible clinical team and where performed will be by standard laboratory diagnostic testing.

A stool sample and/or rectal swab will also be taken from patients in the control group and stored for testing at a later date using the FilmArray GI panel. Samples will be taken on enrolment, frozen and stored, and run on the FilmArray at least 30 days after collection. The results will not influence patient care but is scientifically important as it will allow a direct comparison of diagnostic yield between the groups.

For both control and intervention groups:

Clinical and demographic data will be collected by the study team at the time of enrolment. After patients have been discharged or after 30 days (whichever is soonest), clinical data may be collected retrospectively from electronic and physical case notes, including electronic prescribing which will allow data relating to outcome measures to be recorded by the study team. These include: antibiotic use, duration of hospitalisation, isolation facility use, time to diagnoses and test turnaround time, in addition to safety outcomes and in line with all pre-specified outcome measures. All data will be entered onto a standardised case report form and entered into a secure database.

Participants may be approached for blood sampling (a maximum of 21mls) and additional stool samples and/or rectal swabs and/or vomitus samples to be stored for further study including immunological and pathogen sequencing. All samples left-over from testing may be used for further study. Participant consent for this is included in the consent form.

A participant experience and/or satisfaction survey may be collected from participants after their involvement in the trial.

6. Recruitment / screening / inclusion / exclusion criteria

Recruitment and Screening

Eligible patients in the acute medical unit (AMU), acute surgical unit (ASU) and emergency department (ED) and inpatient wards will be identified by research staff who will regularly review the comprehensive admissions IT systems daily.

Inclusion Criteria

- Aged 18 years or over.
- Has the capacity to give informed, written consent and is able and willing to adhere to the study procedures
- Is a patient in Southampton General Hospital ED, AMU, ASU or inpatient ward
- Can be recruited to the study

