The company product information sheet states "The FilmArray Gastrointestinal (GI) Panel tests for common gastrointestinal pathogens including viruses, bacteria and parasites that cause infectious diarrhea. *(sic)* The integrated FilmArray system brings sample to results in about an hour, with only 2 minutes of hands-on time."

The peer-reviewed published evidence relating to the diagnostic accuracy of the FilmArray Gastrointestinal Panel is discussed in the 'Background' section.

8. Analysis

The retrospective review of medical records will allow comparison of participants who received the rapid diagnostic test and controls managed with standard clinical care.

Primary outcome measure

• Duration of time in a side room

Secondary and exploratory outcomes

- Duration of time in a side room for pathogen positive patients
- Duration of time in a side room for pathogen negative patients

- Proportion of patients isolated in a side room
- Proportion of pathogen positive patients isolated in a side room
- Proportion of pathogen negative patients isolated in a side room
- Proportion of pathogen negative patients de-isolated
- Proportion of pathogen positive patient de-isolated
- Time to patient isolation in a side room
- Time to de-isolation in pathogen negative patients
- Proportion of patients treated with antibiotics
- Proportion of patients with bacterial gastroenteritis treated with antibiotics
- Proportion of patients without bacterial gastroenteritis treated with antibiotics
- Time to treatment with antibiotics
- Duration of antibiotics
- Duration of hospitalisation
- Proportion of patients with a pathogen detected
- Proportion of patients with bacterial pathogen detected
- Time to diagnosis
- Missed diagnoses
- Other medication use, complications (including acute kidney injury), ICU admissions, 30 day mortality, representation and readmission.
- Concordance between results obtained from rectal swab and stool culture
- Time from sampling to availability of results (Turnaround time)
- Patient satisfaction scores (using the modified NHS Adult Inpatient Survey Questionnaire 2016)

Sample size and power calculation

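### Specimen rules differ by arm after open-label allocation, so comparable pathogen status is not secured for the secondary yield, missed-diagnosis and status-split outcomes

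*Protocol*

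**What the plan says.** Protocol section 5 gives each arm its own sampling text.

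- **Intervention arm.** Stool is the default: "In the event of the patient being unable to provide a timely stool sample, a rectal swab will be obtained". If a swab was "tested initially, a stool sample will be subsequently obtained at the earliest opportunity and then tested and the results checked to ensure concordance". A failed run is repeated on the same sample, and "if there is insufficient sample left, further samples may be taken if the participant consents".
- **Control arm.** "A stool sample and/or rectal swab will also be taken from patients in the control group and stored for testing at a later date". On timing: "Samples will be taken on enrolment, frozen and stored, and run on the FilmArray at least 30 days after collection". The text gives no order of preference between specimens, no later stool after a swab and no rule for a failed run.

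The same paragraph gives the purpose of testing controls: "it will allow a direct comparison of diagnostic yield between the groups".

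Section 8 then lists, under secondary and exploratory outcomes, measures that depend on pathogen status, such as "Duration of time in a side room for pathogen negative patients". It also lists agreement between rectal swab and stool results as an outcome in its own right.

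**The concern.** Running the same panel in both arms makes yield comparable only if the material put on the panel is obtained in the same way. As written it is not. A patient in the intervention arm without a timely stool ends up with a swab and a stool result. A control in the same position may have a swab alone. Staff may also use swabs more freely in controls, because nothing asks for stool first and they know the allocation when they take the sample.

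If swabs miss some pathogens that stool would show, fewer control infections are found and some infected controls are classed as negative. The protocol cannot assume that the two specimens are interchangeable, since it lists their agreement as something to be measured.

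Twelve listed outcomes depend on this ascertainment: seven split by pathogen positive or negative, two split by bacterial gastroenteritis, two yield proportions, and missed diagnoses. They include de-isolation measures of the kind that version 2.0 added.

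**Working it through.** The protocol states no figure on this point, so there is none to reproduce. The check sets the rules side by side and then illustrates what the difference could do.

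| Step | Intervention | Control |
|---|---|---|
| First specimen | Stool; swab if no timely stool | Stool, swab or both; no order stated |
| After a swab | Later stool obtained and run | Nothing stated |
| After a failed run | Repeat; further sample possible | Nothing stated |
| When run | At point of care, result in about 1 hour | Frozen, at least 30 days later |

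**Inputs**

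- π, panel positivity on stool: 33.3% or 54%, the two FilmArray figures in the section 3 background.
- f, share of patients whose enrolment specimen is a swab only (fI intervention, fC control): assumed, 10-50%.
- s, sensitivity of a swab relative to stool: assumed, 0.7-0.9.
- r: 1 if the later stool counts towards pathogen status, 0 if it does not. The protocol does not say.

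The model takes stool as the reference and ignores false positives. A control who gives both specimens counts as having stool.

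**Formulas**

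- Intervention positivity = π × [(1 − fI) + fI × (s + (1 − s) × r)]
- Control positivity = π × [(1 − fC) + fC × s]
- Gap (intervention minus control) = π × (1 − s) × [fC − fI × (1 − r)]
- Infected share of control negatives = π × fC × (1 − s) / [1 − π + π × fC × (1 − s)]

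**Equal swab shares, later stool counted (r = 1).** The gap reduces to π × f × (1 − s).

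| π | f | s | Gap | Infected share of control negatives |
|---|---|---|---|---|
| 0.333 | 0.1 | 0.9 | 0.333 × 0.1 × 0.1 = 0.3 points | 0.0033/0.6703 = 0.5% |
| 0.333 | 0.5 | 0.7 | 0.333 × 0.5 × 0.3 = 5.0 points | 0.0500/0.7170 = 7.0% |
| 0.54 | 0.1 | 0.9 | 0.54 × 0.1 × 0.1 = 0.5 points | 0.0054/0.4654 = 1.2% |
| 0.54 | 0.5 | 0.7 | 0.54 × 0.5 × 0.3 = 8.1 points | 0.0810/0.5410 = 15.0% |

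The corresponding share in the intervention arm is 0%, because the later stool corrects every swab miss in this model. In a control arm of 150, gaps of 0.3 to 8.1 points are about 0.5 to 12 patients.

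**Equal swab shares, first specimen sets status (r = 0).** The bracket becomes fC − fI = 0, so the gap is 0 for every π and s. It is also 0 whenever s = 1.

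**Unequal swab shares (fI = 0.1, fC = 0.6, s = 0.7).**

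- Later stool counted: 0.333 × 0.3 × 0.6 = 6.0 points, and 0.54 × 0.3 × 0.6 = 9.7 points.
- First specimen sets status: 0.333 × 0.3 × 0.5 = 5.0 points, and 0.54 × 0.3 × 0.5 = 8.1 points.

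A first-specimen definition is therefore not enough if swabs are used more often in controls. The collection rule must be aligned as well.

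**The case against.** The strongest reply is that the control wording may be shorthand. The synopsis and study overview use the same loose phrase, allowing either specimen or both, for the intervention arm, so staff may in practice sample both arms alike. The phrase also lets a control give both specimens, and nothing says that controls can be sampled only once. The purpose given for the later stool is a concordance check, and no text lets it change a patient's status. Eligible diarrhoea means at least three loose stools for at least a day, so swab-only patients may be few, although patients with vomiting alone can enter. Finally, which result defines status is an analysis definition that a statistical analysis plan may hold.

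Most of this stands, and it limits the size of the problem. It does not remove it. The detailed section 5 text is what staff will follow, and there the rules differ. An analysis plan can define status, but it cannot change which specimen was taken from a control.

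Three stronger readings are tempting and are not supported:

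- **The pathogen-positive and pathogen-negative groups cannot be compared at all.** Only patients without an enrolment stool are affected, and the gap can be zero.
- **Side-room time in negative patients is biased towards the test by a known amount.** That would need an assumed extra stay for every missed control infection. Control panel results do not influence care, so a miss on the stored sample does not itself keep anyone isolated.
- **The missing failed-run rule for controls adds false negatives.** A failed run gives no result, not a negative one, and silence on repeats does not forbid them.

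**Conclusion.** The point holds as one of unsecured comparability, not of demonstrated bias. The written specimen rules differ by arm, the specimen is chosen with allocation known, and the protocol nevertheless claims a direct comparison of yield. The outcomes at risk are the secondary yield, missed-diagnosis and status-split measures. The primary outcome is measured in all patients and is untouched, as are the other whole-group outcomes that do not use pathogen status.

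The size cannot be known from the protocol, which gives neither the swab share nor the sensitivity of a swab. It is nil if swabs match stool, or if swab shares are equal and the first specimen sets status. Under the assumed ranges, with equal swab shares and the later stool counted, control yield is about 0.3 to 8 points too low, and 0.5% to 15% of control negatives would be infected. Heavier swab use in controls would raise the upper figures somewhat.

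**What to change.** Change section 5 so that both arms follow one rule at enrolment: stool first, with a swab only when no timely stool is available. State that, for every between-arm comparison, pathogen status is the panel result on the first valid enrolment specimen. Use the later stool in the intervention arm only for the swab-stool concordance outcome. Report specimen type by arm, so that any remaining imbalance in swab use can be seen.

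Both parts are needed. The common rule brings swab shares together, and the status definition removes the effect of the retest. With equal shares and first-specimen status, the modelled gap is 0 at every positivity and sensitivity.

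The cost is protocol wording and one data item; no extra samples or panels are required. Storing and running follow-up stools for swab-only controls would be an alternative, but it needs added resources and is not necessary. The downside is that a few infections found only on the later stool would count as negative in the between-arm comparison. Control samples would still be frozen for at least 30 days before testing. The effect of that cannot be computed from the protocol and should be stated as a limitation.

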A stool sample from a patient with acute diarrhoea presenting to hospital in England would conventionally undergo a range of laboratory testing methods for different pathogenic organisms. The key methods include microscopy, culture, enzyme immunoassay and PCR.⁹ These methods vary in their turnaround times but culture takes several days to generate a result to clinicians. These slow turnaround times mean that patients presenting with suspected gastroenteritis are isolated and often treated with antibiotics empirically leading to unnecessary isolation facility use in those without infection and antibiotic usage in those without bacterial aetiology.

In addition, conventional diagnostic testing is not comprehensive and is insensitive for many pathogens leading to many missed diagnoses and lack of confidence in a negative result.

Potential benefits of molecular point-of-care testing in acute gastroenteritis

Improved pathogen detection compared to conventional testing

A pan-European observational study showed the pathogen detection rate in stool samples from patients with gastroenteritis could be improved from 18% using traditional methods, to 54% using the multiplex rapid PCR FilmArray Gastroenteritis Panel. Site selection bias, a mix of adult and paediatric and inpatient and outpatient populations and heterogeneous local testing methods weaken the findings. Nevertheless, this multicentre, cross-sectional study clearly shows a wide spectrum of pathogens were detected; 20 different GI pathogens were detected, out of 22 tested for, in around 700 stool samples.¹⁰

Other studies have suggested similar improvements in diagnostic yield, including a USbased study of 230 prospectively collected stool samples, with 8.3% positivity with conventional diagnostics compared to 33.3% positivity with the FilmArray GI panel. Again, a broad range of pathogens were observed.¹¹

A paediatric-based study comparing the aetiologic yield of standard-of-care microbiologic testing ordered by physicians with that of the multiplex FilmArray GI panel, showed that identification of a pathogen increased from 46% to 65%.¹² This suggests a syndrome-based approach to testing may be clinically beneficial.

Decreased length of hospitalisation

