In a single pre-and post-implementation observational study in a hospital setting, a rapid molecular test for *Clostridium difficile*, led to faster turnaround times compared with conventional toxin assays and a decrease in the length of hospitalisation.¹³

Reduced and directed use of antibiotics

A single-centre non-randomised study in France demonstrated that rapid molecular testing for *C.difficile* results in faster results compared to conventional tests and speeds up initiation of appropriate antimicrobial therapy.¹⁴

More appropriate use of isolation facilities

With the lack of diagnostic yield and slow turnaround time of current testing methods, patients with infectious gastroenteritis may not be appropriately isolated, risking spread of disease. One US study suggested that 60% of patients with gastroenteritis, who were eventually found to have had an infectious aetiology, were never placed in appropriate isolation during hospitalisation. In addition, just over 20% of isolated patients ultimately had negative test results and so could have been removed from isolation facilities.¹⁵ A UK study suggested that half of all inpatients with potentially infectious gastroenteritis may have the opportunity for earlier de-isolation if tested with a rapid multiplex molecular test compared to routine care.¹⁶ There was a significant large cost saving associated with this from health economic modelling.¹⁷

A systematic review has noted that POCTs for norovirus have the potential to improve infection control measures but that mediocre sensitivity of the tests and a small number of studies limit this conclusion.¹⁸

Multiplex PCR therefore has the potential to rationalise and improve the use of valuable isolation facilities, improved the flow of patients through acute areas and potentially to reduce costs.

FilmArray Gastrointestinal Panel

The FilmArray Gastrointestinal (GI) Panel is FDA-cleared and CE-marked multiplex rapid PCR (molecular) system. Specific targets and operating information are listed in a dedicated section in this protocol below. Specificity and sensitivity for a wide range of pathogen detected is close to 100%.^{11,19},²⁰

Point-of-care testing in the wider context

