 - within a 48 hour period of first triage by ED staff OR
 - within a 48 hour period of arrival on AMU or ASU or inpatient ward (if admitted directly to an inpatient ward)
- Has an acute diarrhoeal illness and /or vomiting*
- Has a duration of illness less of than or equal to 14 days

*An episode of acute diarrhoea is defined as the passage of at least 3 loose stools for at least 1 day.

Exclusion Criteria

- Patients not fulfilling inclusion criteria
- A palliative approach being taken by the treating clinicians
- Previously included in this study and re-presenting within the last 30 days after hospital discharge
- Declines to give stool sample and/or rectal swab

Involvement in other research trials is not necessarily an exclusion criterion. Concurrent, prior or subsequent enrolment in an observational study is not expected to be an exclusion criterion, except at the discretion of the PI.

7. Further information regarding the FilmArray Gastrointestinal

Panel

The FilmArray Gastrointestinal Panel is a rapid diagnostic test that uses nested RT-PCR followed by melt curve analysis to detect 22 targets. The apparatus takes about an hour to give results. It is deployable as a point-of-care test and the units will be housed in the acute areas for this study. The manufacturers are BioFire Diagnostics, [name] and their website is www.BioFireDx.com. BioFire Diagnostics is owned by bioMérieux. The FilmArray Gastrointestinal Panel is CE IVD marked and FDA (USA) approved.

The following targets are detectable:

Bacteria

Campylobacter (jejuni, coli and upsaliensis) Clostridium difficile (toxin A/B) Plesiomonas shigelloides Salmonella Yersinia enterocolitica Vibrio (parahaemolyticus, vulnificus and cholerae) Vibrio cholerae Diarrheagenic *E. coli/Shigella*: Enteroaggregative *E. coli* (EAEC) Enteropathogenic *E. coli* (EPEC) Enterotoxigenic *E. coli* (ETEC) *It/st* Shiga-like toxin-producing *E. coli* (STEC) *stx1/stx2 E. coli* 0157 Shigella/Enteroinvasive E. coli (EIEC)

Parasites

Cryptosporidium Cyclospora cayetanensis Entamoeba histolytica Giardia lamblia

Viruses

Adenovirus F 40/41 Astrovirus Norovirus GI/GII Rotavirus A Sapovirus (I, II, IV and V)

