This will be performed by the research team in conjunction with a dedicated medical statistician from the University of Southampton. Patients tested with the rapid molecular diagnostic test will be compared with patients treated using standard clinical care using standard descriptive and comparative statistical methods using Prism (GraphPad Software Inc; La Jolla, California) and SPSS (SPSS, Inc; Chicago, Illinois). The primary outcome measure of duration of time in side room isolation will be compared using the students t-test or Mann-Whitney U test as appropriate. The effect of group (intervention or control) on the primary outcome will be further assessed using logistic regression to control for demographics (age, sex) and relevant clinical variables.

Analysis will be by intention-to-treat. No interim analysis is planned. Trial results will be reported in accordance with the CONSORT statement. Missing data was minimal in the Cl's previous molecular POC RCT in secondary care and therefore expected to not be a significant issue.

11. Ethics and Approvals

Declaration of Helsinki

The Investigators will ensure that this study is conducted according to the principles of the current revision of the Declaration of Helsinki.

ICH Guidelines for Good Clinical Practice

The Investigators will ensure that this study is conducted in full conformity with the ICH Good Clinical Practice (GCP) and local regulatory requirements.

Informed Consent

Written, informed consent will be obtained, as per the informed consent form.

Submissions to HRA, REC and local R&D

The protocol, informed consent form, participant information sheet and GP letter (and any other document requested) will be submitted to the Health Research Agency (HRA) for their processes including Regional Ethics Committee (REC) for written approval, and the study will not commence until REC all necessary HRA approvals are in place. The Chief Investigator will submit and, where necessary, obtain approval from the REC for all subsequent substantial amendments to the protocol and informed consent document. Local R&D approval will be confirmed prior to study commencement.

Participant Confidentiality

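### The primary outcome, side-room time, has no stated start, so with recruitment up to 48 hours after arrival it does not exclude time before randomisation that the test cannot affect

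*Protocol*

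**What the plan says.** - **Recruitment window.** Protocol section 6 (Inclusion Criteria) accepts emergency department patients "within a 48 hour period of first triage by ED staff OR"; the alternative route, for those on the units and wards, is recruitment "within a 48 hour period of arrival on AMU or ASU or inpatient ward". Section 5 (Randomisation) places allocation after screening and consent. The panel result follows about an hour after the sample is run.
- **Primary outcome.** Section 8 lists "Duration of time in a side room" and nothing more. Section 10 says that "duration of time in side room isolation will be compared using the students t-test or Mann-Whitney U test as appropriate". Neither place gives a start, an end or a rule for time before randomisation.
- **Secondary outcome.** Section 8 also lists "Time to patient isolation in a side room", again without a time origin.
- **Isolation before testing.** Section 3 (Conventional testing) says of current practice that "patients presenting with suspected gastroenteritis are isolated and often treated with antibiotics empirically".
- **Adjusted analysis.** Section 10 plans a logistic regression of the primary outcome on group, controlling for age, sex and clinical variables judged relevant. Side-room status at randomisation is not named.

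**The concern.** The test can change side-room use only after randomisation, sampling and a run. A patient isolated on arrival and enrolled a day later already has a day in a side room that neither arm can alter. The planned control mean is 3 days, so a window of up to 2 days is large beside it.

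Three things are at stake:

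- Unmodifiable time adds variance to the primary comparison.
- The planned 1-day saving has to come wholly from the part of the stay after randomisation.
- Time to isolation includes events that happened before randomisation, on which the allocation can have no effect.

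The trial is open-label and the data are taken retrospectively from case notes. A start point left open could therefore be chosen after allocation is known.

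**Working it through.** **Inputs from the protocol** (section 8, Sample size and power calculation): 141 per group, 90% power, significance level 0.05, means of 3 and 2 days, SD stated as 6.7 days. Sidedness is not stated; two-sided is assumed.

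**Inputs assumed**, because the protocol gives no figure: the mean side-room time before randomisation, *m*, and its standard deviation, *s*.

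**Step 1: the plan's own figure.** n per group = 2 × SD² × (1.960 + 1.282)² / difference².

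- With SD 6.7: 2 × 44.89 × 10.51 / 1 gives 944 per group, not 141.
- With variance 6.7 (SD 2.59): 2 × 6.7 × 10.51 / 1 gives 141.

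So 6.7 looks like a variance labelled as an SD. That is a separate and larger problem. Here it means that each result has to be shown on both readings.

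**Step 2: power at 141 per group.** Power = Φ(difference × √(141/2) / SD − 1.960), with √70.5 = 8.40.

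- SD 2.59, difference 1: Φ(3.24 − 1.96) = 90.0%.
- SD 6.7, difference 1: Φ(1.25 − 1.96) = 24.0%.

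**Step 3: noise.** The planning SD comes from the first 100 patients. If their side-room time was counted without excluding time before randomisation, the SD already contains that component, and the relevant quantity is the gain from removing it. Assume the component is uniform over 0 to 2 days and independent of later time: *s* = 2/√12 = 0.58 day.

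- SD 2.59 becomes √(2.59² − 0.58²) = 2.52, and power rises from 90.0% to 91.4%.
- SD 6.7 becomes √(6.7² − 0.58²) = 6.68, and power moves from 24.0% to 24.1%.

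The largest SD possible on a 0 to 2 day range is 1.0, with half the patients at 0 and half at 2. At SD 2.59 that extreme would give about 94%.

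**Step 4: share of modifiable time.** A 1-day saving out of (3 − *m*) days is 33% at *m* = 0, 40% at 0.5, 50% at 1 and 100% at 2.

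**Step 5: dilution.** Suppose the effect is a one-third cut in post-randomisation time only. The difference in means is then (3 − *m*)/3.

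| *m* (days) | Difference (days) | Power, SD 2.59 | Power, SD 6.7 |
|---|---|---|---|
| 0 | 1.00 | 90% | 24% |
| 0.25 | 0.92 | 84% | 21% |
| 0.5 | 0.83 | 77% | 18% |
| 1.0 | 0.67 | 58% | 13% |

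If a full 1-day absolute saving is achieved, there is no dilution. Starting the count at randomisation does not by itself restore a diluted difference. Time before randomisation has the same expected value in both arms, so total and post-randomisation time have the same difference in means. What it removes is the noise in step 3, and it shows whether the planning difference is realistic for the time that can change.

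**The case against.** The case against is substantial, and much of it stands.

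- **The protocol does not say that all side-room time counts.** A reader might infer this, but the start is simply undefined. Derivation rules often sit in a statistical analysis plan, which was not available here. What remains is that the definition as written does not exclude time before randomisation.
- **A reader might infer that patients are often already isolated when randomised.** No proportion is given. The section 3 statement is general background. The same section cites a US study in which 60% of patients with an infectious cause "were never placed in appropriate isolation during hospitalisation". Having time to isolation as an outcome also implies that some patients are not isolated at enrolment.
- **A reader might infer bias.** Time before randomisation is a baseline quantity, balanced in expectation by 1:1 allocation.
- **A reader might add the extra variance to the planning variance.** With SD 2.59 and *s* of 0.58 to 1.0 day, an exact t-test calculation gives a fall from 89.8% to between 88.4% and 85.4%. That holds only if the pilot SD excludes this time, which the protocol does not say. Otherwise it counts the same variation twice.
- **A reader might take the adjustment to be for age and sex alone.** Section 10 also allows relevant clinical variables, so side-room status at randomisation could be included. It is just not named.
- **Whole-admission side-room time is a defensible resource measure** in a pragmatic trial with a health economic aim. That is a reason to report it, but not to leave the primary outcome without a start point.

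**Conclusion.** The point holds as one of precision and definition. A recruitment window of up to 48 hours, together with an outcome that has no time origin, lets unmodifiable side-room time into the primary outcome and pre-randomisation events into time to isolation. It does not bias the comparison.

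The noise cost is small: about one percentage point of power with SD 2.59 and a uniform 48-hour component, and practically nothing with SD 6.7 as written. The dilution cost could be larger, with power of about 84% to 77% for a mean of 0.25 to 0.5 day before randomisation. That applies only if the effect is proportional to post-randomisation time, the 3-day mean includes earlier time, and SD 2.59 is the right reading. None of these can be confirmed from the protocol. This is a worthwhile and cheap improvement; it does not undermine the design.

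**What to change.** 1. Define the primary outcome as side-room time from randomisation to the first of discharge, death or day 30, with zero for patients never in a side room in that period.
2. Name side-room status at randomisation (yes/no) as a covariate, in an adjusted model suited to a duration. The logistic regression in section 10 is not one.
3. Analyse time to isolation from randomisation, only in patients not yet isolated at that point.
4. Report whole-admission side-room time descriptively, for resource use.

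The cost is mainly wording. Section 5 already plans to collect isolation facility use from the case notes, though the times of entering and leaving a side room need to be recorded relative to randomisation. The one real downside is that the 3-day and 2-day planning means and the SD must be re-derived from the pilot on the same time origin, and the sample size checked against them.
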